Determine the impact of upper airway stimulation on peripheral arterial tonometry ratio related to obstructive episodes in this cohort of patients with moderate-severe obstructive sleep apnea

Hypothesis: The peripheral arterial tonometry ratio related to obstructive episodes will be improved with increasing levels of upper airway stimulation

Aim 2a

Determine the impact of upper airway stimulation on flow mediated dilation in this cohort of patients with moderate-severe obstructive sleep apnea

Hypothesis: The flow mediated dilation parameters will be improved at therapeutic levels of upper airway stimulation and returned to pre-operative levels after 30-day withdrawal period

Aim 2b

Determine the impact of upper airway stimulation on peripheral arterial stiffness in this cohort of patients with moderate-severe obstructive sleep apnea

Hypothesis: The peripheral arterial stiffness parameters will be improved at therapeutic levels of upper airway stimulation and returned to pre-operative levels after 30-day withdrawal period

Aim 2c

Determine the impact of upper airway stimulation on 24-hour ambulatory blood pressure in this cohort of patients with moderate-severe obstructive sleep apnea

Hypothesis: The 24-hour ambulatory blood pressure will be improved at therapeutic levels of upper airway stimulation and returned to pre-operative levels after 30-day withdrawal period

Aim 2d

Determine the impact of upper airway stimulation on serum biomarker profile in this cohort of patients with moderate-severe obstructive sleep apnea

Hypothesis: The serum biomarker profile will be improved at therapeutic levels of upper airway stimulation and returned to pre-operative levels after 30-day withdrawal period

6. Study Design and Methods

Each participant will undergo three sets of blood testing. Each set of testing will require travel to the Emory Clinical Cardiovascular Research Institute (ECCRI) facility at Woodruff Memorial Research Building on Clifton Campus. The subjects will be provided directions, lunch and parking vouchers for each visit. The subject will be registered at the EECRI facility each time and undergo fasting bloodwork.

Study Timeline

- Post-operative appointment: obtain consent for study enrollment (Day 1)
- WatchPAT baseline home sleep test (Night 1)
- Baseline 24-hour ambulatory blood pressure monitoring (Day 2-3)
- Baseline serum biomarkers/vascular testing (Day 15)
- Device Activation (Day 15)
- In-lab Polysomnography Titration (Day 45)

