This study is designed to learn more about the cardiovascular improvement with this form of treatment of obstructive sleep apnea. The study results may be used to help others in the future.

Information to be Collected

- Medical information about you including your medical history and present/past medications.
- Results of exams, procedures and tests you have before and during the study.

Specimens to be Collected

- Blood samples (before, during and after sleep apnea treatment)

Randomization and Blinding

There will be no randomization. Interpretation of all tests (sleep tests, ambulatory blood pressure monitoring, vascular test and blood tests) will single-blinded.

7. Data Sample Information

We will obtain a blood sample (about 1/2 cup) from you and store the blood for future analysis. The blood sample may be obtained by a nurse or physician as part of other blood draws you are undergoing during your visit(s). A study ID number will be used to link your blood sample to your other information. The DNA (genetic material) in your blood sample will be isolated and stored for future studies. Permanent cells may be created. Once DNA is isolated, it can be duplicated indefinitely for future research. Serum and plasma from your blood samples will also be stored and analyzed for a variety of biochemical factors. If you are less than 60 years old an extra tube of blood (about 1/2 tablespoon) will be collected. This extra tube of blood will be used to look at a special type of cell in your blood. This type of blood cell may help explain the difference between young women and young men with heart disease.

8. Community Participation

Not applicable

9. Participant Selection

Requested sample size: 50 subjects

Expected refusal/withdrawal: 10 subjects

Subjects completing study: 40 subjects

Inclusion criteria: All patients are English-speaking, greater than 18 years old and able to give informed consent. HGNS inclusion criteria per FDA require an AHI ≥ 20 on recent sleep testing, unable to use positive airway pressure therapy, BMI < 32 , without circumferential collapse on drug-induced sedated endoscopy. In essence, the inclusion criteria are those patients who have undergone HGNS implantation.

Exclusion criteria: active smokers, unstable and untreated coronary or peripheral artery disease, alpha-blockers, severe and inadequately controlled arterial hypertension.

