Subject recruitment plan: All patients in the cohort will have undergone implantation of hypoglossal nerve stimulator by the principal investigator, [name], at the Sleep Surgery Center at Emory Midtown. At their 2-week post-operative appointment, they will be approached by the research coordinator at the Emory Sleep Center regarding participation in the study.

Screening for eligibility: Eligible subjects will be identified based on a clinical chart review by the principal investigator / surgeon, [name].

Procedures when a subject withdraws from the study:

1. Once the subject expresses that he/she would like to withdraw, no further information will be collected from the subject
2. Existing data will be utilized for appropriate analyses
3. These changes will be reflected in the intention-to-treat analysis

10. Informed Consent Process

The consent process will be done in person by the research assistant.

The research assistant will remain in the patient room for an extended period of time to ensure the subject's patients are adequately answered. We will deliberately schedule these patients as the last slot in the morning clinic allowing greater than 30 minutes before the first patient in the afternoon clinic. The research assistant will also ask the subject to repeat the procedures and timeline involved in this study.

The informed consent will allow for the subject to "opt out" of certain aspects of the study. The choices will be captured in the informed consent layout.

11. Incidental Findings

We anticipate incidental findings for the 24-hour blood pressure monitoring. We will set the following parameters for which the patient will be notified and asked to contact his/her primary care physician:

- Systolic BP > 200mm Hg for greater than 60 minutes of recording time
- Diastolic BP > 160mm Hg for greater than 60 minutes of recording time

The consent will include wording to indicate that he/she may be contacted if these results are seen. The principal investigator and treating physician ([name]) will call the patient to inform him/her of the findings. The subject will be provided the option to withdraw from the study at that time.

12. Compensation

The subject will not be offered payment for being in this study. However, we will provide mailing costs for return of sleep testing and blood pressure equipment. The subject will

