also be provided lunch and parking vouchers for each time (3 in total) that he/she undergoes cardiovascular testing. The subject will not be responsible to pay for any cardiovascular testing as this is being done outside routine clinical care.

13. Statistical Analysis

With 40 subjects, we will have 89% power to detect a difference of 0.1 in the PAT ratio (primary outcome) with a standard deviation of 0.2 and alpha of 0.05.

Each subject will have a baseline PAT ratio derived from the average of the 10 obstructive events without stimulation (Aim 1). The PAT ratios at each stimulation level (5-7 stimulation levels based on previous experience) will be averaged from 5 obstructive events at each level. With greater than 30 data points per individual, linear regression will be performed for each subject with stimulation level as the main effect variable and PAT ratio as the outcome variable. We will determine if stimulation level is positively associated with PAT ratio. We will also perform linear regression, in a similar manner, from the combined values of the cohort to determine an effect at the sample level.

An interim analysis will not be performed as the primary outcome variable is largely observational (non-interventional); thus, the findings are expected during the treatment of moderate-severe obstructive sleep apnea

14. Data Safety and Monitoring Board

A DSMB will not be required. Access to this database will be restricted by a database manager and will be password protected. The only individuals who will be able to see patient identifiers, like name, address, and social security number, will be the Principal Investigator, research coordinators, recruiters and the database managers. Other investigators will have different passwords that will provide restricted access to the database. Those with restricted access will be able to query the database for scientific information/variables, but will not be able to view information on patient identifiers such as name, address, and social security number. If investigators with restricted access want to conduct studies which require them to obtain patient identifiers so that patients can be contacted for follow-up information/follow-up visits, these investigators will have to submit a separate protocol to IRB to get permission to obtain patient identifiers and contact patients.

15. Confidentiality

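### The combined-cohort Aim 1 regression states no subject term, and Section 13 contradicts itself on what counts as a data point

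*Combined protocol and SAP*

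**What the plan says.** Section 13 (Statistical Analysis) describes the Aim 1 analysis in four steps.

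- Baseline: "Each subject will have a baseline PAT ratio derived from the average of the 10 obstructive events without stimulation".
- Each of 5-7 stimulation levels: the PAT ratio "will be averaged from 5 obstructive events at each level".
- Per subject: "With greater than 30 data points per individual", a linear regression of PAT ratio on stimulation level.
- Cohort: a similar linear regression "from the combined values of the cohort to determine an effect at the sample level".

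No subject effect, clustering adjustment or weighting is stated. Nothing says what happens at a level with fewer than 5 obstructive events. The nearest rule, in Section 9, is "Existing data will be utilized for appropriate analyses", and it applies to subjects who withdraw.

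The Aim 1 hypothesis in Section 5 is "The peripheral arterial tonometry ratio related to obstructive episodes will be improved with increasing levels of upper airway stimulation". Section 9 says the device criteria "require an AHI ≥ 20 on recent sleep testing". Section 4 reports a marked improvement in polysomnography indices with this therapy but gives no figure.

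**The concern.** Each subject contributes many values to the combined regression. Subjects will differ in their baseline PAT ratio and probably in how much it changes with stimulation. An ordinary regression that ignores this gives a standard error that does not match the real uncertainty. The direction of the error depends on whether events or level means are pooled, which is the point on which Section 13 contradicts itself.

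There is a second, conditional problem. The outcome exists only on obstructive events, and the therapy is expected to reduce them. If event loss at the higher levels goes with the size of a subject's PAT gain, the combined values at those levels come from a selected set of subjects, and the combined slope moves. How far it moves depends on how short levels are handled, and that choice could be made after the data are seen.

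**Working it through.** **1. The plan's own figure.** Section 13 gives 40 subjects, a difference of 0.1, SD 0.2 and alpha 0.05. The two-sided normal approximation is Φ(0.1/(0.2/√40) − 1.96) = Φ(3.162 − 1.960) = Φ(1.202) = 0.885, against the stated 89%. This is power for a mean difference across 40 subjects. No slope or event count enters it, so the point below leaves it unchanged.

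**2. The unit of analysis (Section 13 figures only).**

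| Levels | Level means plus baseline mean | Single events |
|---|---|---|
| 5 | 1 + 5 = 6 | 10 + 25 = 35 |
| 6 | 1 + 6 = 7 | 10 + 30 = 40 |
| 7 | 1 + 7 = 8 | 10 + 35 = 45 |

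Only single events exceed 30, and only if nearly every level yields 5. With 5 levels, one level without events leaves exactly 30.

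**3. The interval when no event is missing.** Assumed inputs: level scaled so that x runs from 0 (baseline) to 1 (top level), 6 levels, n = 40, event SD 0.2, between-subject intercept SD σa = 0.1, slope SD σb = 0.10 or 0, all independent. Let d = x − mean x, S = Σd² per subject, and v = the error variance of each point.

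- Actual variance of the combined slope: [σb² + Σd²v/S²]/n
- Variance that ordinary regression reports, approximately: [σa² + σb²·mean(x²) + mean(v)]/(nS)

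Events: S = 4.983, mean(x²) = 0.316, v = 0.04. With σb = 0.10, actual = (0.01 + 0.04/4.983)/40 = 0.000451 and reported = (0.01 + 0.00316 + 0.04)/(40 × 4.983) = 0.000267.

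Means: S = 0.778, mean(x²) = 0.361, v = 0.004 at baseline and 0.008 at each level (mean 0.00743). With σb = 0.10, actual = (0.01 + 0.00863)/40 = 0.000466 and reported = (0.01 + 0.00361 + 0.00743)/(40 × 0.778) = 0.000676.

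| Unit pooled | Slope SD | Actual SE | Reported SE | Ratio | Coverage of 95% interval |
|---|---|---|---|---|---|
| Events | 0.10 | 0.0212 | 0.0163 | 0.77 | 0.87 |
| Events | 0 | 0.0142 | 0.0158 | 1.12 | 0.97 |
| Means | 0.10 | 0.0216 | 0.0260 | 1.20 | 0.98 |
| Means | 0 | 0.0147 | 0.0237 | 1.61 | above 0.99 |

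Coverage is 2Φ(1.96 × ratio) − 1. The error can go either way, and no missing event or correlation is needed.

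**4. How often a level might be short.** The documents give no time per level. If one night were split equally, it would be (360 − 30)/7 = 47 min to (420 − 30)/5 = 78 min. With Poisson counts at 47/60/78 min, the chance of fewer than 5 events is 0.11/0.03/0.004 at a residual AHI of 10, 0.64/0.44/0.22 at 5 and 0.98/0.95/0.88 at 2. The chance of none at AHI 2 is 0.21/0.14/0.07.

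**5. The slope when levels are short.** Simulation, all inputs assumed: 1,500 trials of 40 subjects per setting; 5, 6 or 7 levels, the same for every subject within a setting; true slope 0.10 over the full level range, linear; SDs as in step 3; baseline AHI mean 35, SD 12, floored at 20; exponential AHI decay with log-normal spread 0.5. Correlation is between a subject's PAT gain and event loss, and AHI fall is at the top level. The last three columns are the combined slope under each handling of short levels.

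| AHI fall | Correlation | Short levels dropped | Kept, single events | Kept, one mean per level |
|---|---|---|---|---|
| 78-86% | 0.5 to 0.8 | 0.043-0.085 | 0.067-0.093 | 0.083-0.098 |
| 65% | 0.5 to 0.8 | 0.078-0.093 | 0.089-0.097 | 0.097-0.099 |
| 50% | 0.5 to 0.8 | 0.091-0.099 | 0.096-0.100 | 0.099-0.101 |
| 78-86% | 0 | 0.098-0.101 | 0.098-0.101 | 0.098-0.101 |
| 78-86% | −0.5 | 0.116-0.134 | 0.109-0.119 | 0.103-0.110 |

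If recording continues to 5 events, the first row becomes 0.099-0.101. At a 78-86% fall, the unweighted mean of within-subject slopes, with short levels kept, stays at 0.098-0.101 for correlations from −0.5 to 0.8.

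**6. Intervals with short levels.** A second simulation on the same assumed inputs gave combined event-level slopes of 0.072-0.101 with coverage 0.60-0.97, below 0.95 in some settings even at zero correlation. The mean of within-subject slopes, tested across subjects, gave 0.099-0.101 with coverage 0.94-0.96.

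**The case against.** The strongest reply has four parts.

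- **Inputs.** The slope bias needs a limited time per level, a large fall in events and a non-zero correlation, and none of these is in the documents. They do not say that Aim 1 is recorded in one equally split night, or that the Day 45 titration in Section 6 is that recording. This stands. A reader might infer that the plan will understate the effect. The documents do not support that: the bias can be zero, and it can go upward.
- **Plain reading.** Taken literally, 5 events are obtained at every level, and then the slope is not biased. Even without that, an analyst who simply averages the available events loses little slope accuracy. This also stands. Taken alone, the missing short-level rule is mostly missing detail. It does not answer step 3, where every level is complete.
- **Status.** No section calls the combined slope primary. The powered quantity is a PAT difference of 0.1, and the per-subject slopes are little affected when the response is linear. A reader might infer that the 89% power fails, or that 30 points is a validity threshold. Neither follows. The combined fit is nevertheless the only stated route from Aim 1 data to a cohort-level dose-response result.
- **Cost of means.** Forcing level means into the per-subject tests cuts residual degrees of freedom from 33-43 to 4-6. For a true slope of 0.2 with independent events of SD 0.2, power falls from 0.55-0.62 to 0.31-0.43. This stands, and the fix allows for it.

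**Conclusion.** The point holds in this form. The combined regression, as written, ignores that values are clustered within subjects, so its interval is unreliable in either direction. On the assumed variances and complete data, coverage is about 0.87 for events and 0.98 for means. The contradiction between 6-8 and more than 30 points per subject follows from Section 13's own numbers and needs no assumption.

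The shift in slope is conditional. With a linear response there is none at zero correlation, little at a 50% fall in events, and none if recording continues to 5 events. A positive correlation attenuates the slope and a negative one inflates it. The tabulated sizes illustrate what could happen and do not predict what this trial will show. This should be fixed. Confidence is medium, because the size of the effect rests on inputs outside the documents.

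**What to change.** Change Section 13 as follows.

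- Base the sample-level Aim 1 result on the unweighted mean of the within-subject slopes, tested across subjects. Keep the combined regression as supportive.
- State the unit of the slope: per level, or over the full level range. The two differ when subjects have 5-7 levels, since 0.1 over the range is 0.020 per level with 5 levels and 0.014 with 7.
- Compute each slope from equally weighted level means plus the baseline mean. Use up to 5 events per level, keep levels with 1-4 events, and treat levels with none as missing.
- Reconcile the count of more than 30 data points with the unit used. The separate per-subject tests may stay at event level, which avoids the loss of degrees of freedom.
- Report events per level and the number of subjects with too few levels to fit a slope.

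The cost is wording, with no new data or visits. Means from 1-4 events are noisier. Some bias remains if the response is not linear: with a gain only above the middle level and correlations of 0 to 0.8, the proposed slope was 0.085-0.100 against a true 0.10, with coverage as low as 0.90. The combined fit with short levels kept gave 0.082-0.101, so in that setting the proposal is about equal in slope and not better.

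### The pooled cohort regression for Aim 1 (Section 13) treats repeated values from the same subject as independent, so its standard error and p-value are not valid; the regression unit also needs stating.

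*Combined protocol and SAP*

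**What the plan says.** All of this is in Section 13 (Statistical Analysis) unless noted.

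- The baseline PAT ratio is "derived from the average of the 10 obstructive events without stimulation". The ratio at each level ("5-7 stimulation levels based on previous experience") "will be averaged from 5 obstructive events at each level".
- The within-subject model is introduced by "With greater than 30 data points per individual, linear regression will be performed for each subject". Its only stated terms come next: the model is fitted "with stimulation level as the main effect variable and PAT ratio as the outcome variable".
- The cohort model is "linear regression, in a similar manner, from the combined values of the cohort to determine an effect at the sample level".
- Section 5 (Objectives, Aim 1) gives the hypothesis that the cohort model is meant to answer: the PAT ratio "will be improved with increasing levels of upper airway stimulation".

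The documents mention no random effect, subject term, cluster-robust error or two-stage analysis of slopes. They give no event-level, between-subject or slope SD.

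**The concern.** The cohort regression supplies the sample-level answer for Aim 1. It stacks all values from all subjects and fits one line, as if each row came from a different person. With 40 subjects and baseline included, that is 240-320 rows of averages or 1,400-1,800 rows of events. Only 40 subjects carry independent information on how the slope varies between people, so the reported interval and p-value for the main Aim 1 claim could be seriously wrong. Choosing averages or events does not cure this.

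A smaller matter is that the text defines PAT ratios as averages, while the data-point count attached to the regression fits single events. Two analysts could read the within-subject model differently and report different intervals from the same data.

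**Working it through.** **1. The plan's own figure.** Inputs from Section 13: 40 subjects, difference 0.1, SD 0.2, alpha 0.05. Two-sided one-sample (paired) normal approximation: Φ(0.1/(0.2/√40) − 1.96) = Φ(3.162 − 1.96) = 0.885, which rounds to the stated 89%. This calculation uses one difference per subject, so neither point below touches it.

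**2. Data points per subject** (5 to 7 levels; 10 baseline events; 5 events per level).

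| Unit | With baseline | Without baseline |
|---|---|---|
| Averages | 5+1 to 7+1 = 6-8 | 5-7 |
| Events | 10+25 to 10+35 = 35-45 | 25-35 |

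A count above 30 at every number of levels from 5 to 7 occurs only for single events with baseline. Residual df per subject (count minus 2), with baseline, are 4-6 for averages and 33-43 for events.

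**3. Why the pooled standard error is wrong.** Assume each subject has an intercept (SD σb), a slope (SD σs per level) and independent event error (SD σe). Let Sxx be one subject's sum of squared deviations of level from its mean. If all subjects share the same levels:

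- true variance of the pooled slope = (σs² + σe²/Sxx)/40
- variance the pooled fit reports = (residual variance)/(40·Sxx), where the residual variance is about σe² + σb² + σs²·mean(level²).

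The pooled fit thus includes σb², which cancels from the true slope variance, and dilutes σs² over all rows. The two errors act in opposite directions.

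**4. Two worked cases** (events, 7 levels plus baseline, assumed σe = 0.15). Sxx = 700 − 140²/45 = 264.4.

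- *σb = 0.1, slope SD 0.2 over the range (0.2/7 per level).* True SE = √[(0.000816 + 0.0225/264.4)/40] = 0.00475. Residual variance is about 0.0225 + 0.01 + 0.000816 × 15.56 = 0.0452 (0.0447 after allowing for the fitted line). Reported SE = √[0.0447/(40 × 264.4)] = 0.00205. Ratio 0.43; rejection 2Φ(−1.96 × 0.43), about 40%.
- *σb = 0.2, slope SD 0.* True SE = √[(0.0225/264.4)/40] = 0.00146. Residual variance is about 0.0225 + 0.04 = 0.0625 (0.0615 after the same allowance). Reported SE = 0.00241. Ratio 1.65; rejection about 0.1%.

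**5. Full grid.** Assumed event SD 0.15, intercept SD 0.1 and 0.2, slope SD 0, 0.05, 0.1 and 0.2 over the level range, no true mean slope, 40 subjects, baseline included, nominal 5%. Pooled columns are closed form; the last column is from 4,000 simulations per scenario. For varying levels, 13/14/13 subjects have 5/6/7 levels, level is coded as step number, and the slope SD is taken over six levels.

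| Levels | Pooled events | Pooled averages | t-test on subject slopes |
|---|---|---|---|
| Same for all subjects | 0.1-39.6% | 0-9.2% | 4.5-5.7% |
| 5-7, varying by subject | 6.0-45.3% | 0.1-14.5% | 4.8-5.4% |

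With varying levels the intercepts no longer cancel, because subjects with more levels have a higher mean level. Even with slope SD 0, the pooled-event SE ratio is 0.96 (intercept SD 0.1) or 0.92 (0.2), giving 6.0% and 7.1%. Simulating the varying-level pooled fits gives 6.1-45.2% for events and 0.1-14.8% for averages.

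**6. Within-subject test if events are the unit.** At assumed within-level correlation 0 / 0.1 / 0.3, event rows treated as independent reject at about 5 / 12 / 26% with baseline. Unweighted averages stay at 3.8-4.9%.

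**The case against.** *The count already settles the unit.* Largely true. More than 30 points at every number of levels fits only single events with baseline, and averages could be meant as descriptive summaries. A reader might infer an arithmetic error or a contradiction, but the documents do not support that, because a coherent event-level reading exists. What stands is that the unit and the role of baseline must be inferred, against definitions given in terms of averages. That alone would be a wording matter.

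*Pooling can be conservative.* Also true in part. If all subjects share the same levels and differ mainly in overall PAT ratio, the pooled standard error is too large; pooled averages can be conservative with varying levels too. A reader might infer that pooling always inflates false positives, or that there is a known slope SD at which it comes right. Neither is supported: the direction depends on SDs the plan does not give and on whether levels are shared. For pooled events with varying levels, the standard error was too small at every point of the grid.

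*The rates rest on assumed SDs.* They do, and another choice would move them. The defect itself does not depend on the values: no stated feature of the model accounts for repeated values within subject.

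**Conclusion.** The concern holds for the cohort regression. As written, its standard error and p-value are not valid under either unit, and the documents do not allow the size or direction of the error to be fixed in advance. The rates in the working show the possible scale under the assumptions listed there; they are not predictions for this trial. A test on subject slopes holds its level without knowledge of those SDs. The unit point is secondary.

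A reader might also infer that the sample size is undermined. It is not: the 89% concerns a mean difference with one value per subject. The change should be made before analysis, but it alters no data collection.

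**What to change.** **Cohort analysis.** Replace the pooled regression in Section 13 with wording such as:

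> The cohort effect is the mean of the subject-specific slopes, with stimulation level on one stated scale common to all subjects, reported with its 95% CI and a one-sample t-test (df = number of subjects with an estimable slope minus 1).

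The scale (for example step number, amplitude or fraction of the subject's range) must be named, because slopes over 5 and over 7 levels are comparable only on a defined scale. A mixed model with random subject intercept and slope is an acceptable alternative; its estimate can differ slightly from the simple mean when subjects have different numbers of levels.

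**Unit.** State whether the within-subject regression uses level averages or single events, whether the no-stimulation baseline enters as level 0, and the matching count from the table above. If events are used, the per-subject p-values must allow for correlation of events within a level. That removes most of the apparent gain from 4-6 to 33-43 residual df.

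**Cost.** A few sentences in Section 13 and no new data. The subject slopes come from regressions already planned. If averages are chosen, the stated count falls from more than 30 to 6-8 (5-7 without baseline) and per-subject intervals widen, but the cohort test does not use the per-subject df.

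### If the stimulation-off events enter the Aim 1 regression, as Section 13's data count implies, a positive slope cannot separate an on/off effect from a graded one

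*Combined protocol and SAP*

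**What the plan says.** Section 5 words the Aim 1 hypothesis as a graded one: the PAT ratio during obstructive episodes "will be improved with increasing levels of upper airway stimulation".

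Section 13 names the PAT ratio as the primary outcome and gives 89% power with 40 subjects for a difference of 0.1, "with a standard deviation of 0.2 and alpha of 0.05". Each subject has a "baseline PAT ratio derived from the average of the 10 obstructive events without stimulation". The PAT ratio at each of 5 to 7 stimulation levels is the average of 5 events. The analysis sentence follows: "With greater than 30 data points per individual, linear regression will be performed for each subject with stimulation level as the main effect variable". The decision rule is: "We will determine if stimulation level is positively associated with PAT ratio". A similar regression is then run on the combined values of the cohort.

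The section does not say whether the off events are in these regressions, how they would be coded, or which recording supplies them. It gives no on/off term, no analysis restricted to active levels and no check of linearity.

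**The concern.** A single slope over off and active events mixes two contrasts: off against any stimulation, and less against more stimulation among the active levels. Only the second addresses whether the PAT ratio keeps improving as the level goes up. If the off events sit at level 0, the first contrast alone can produce a significant slope. The trial could then report a graded effect on its primary outcome when it has shown only that stimulation does something. Handling the repeated values within subjects correctly does not cure this, because the mixing occurs inside each subject's slope.

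**Working it through.** **1. The plan's power figure.** Inputs from Section 13: n = 40, difference 0.1, SD 0.2, alpha 0.05 (taken as two-sided). For one mean within-subject difference, normal approximation: Φ(0.1/0.2 × √40 − 1.96) = Φ(3.162 − 1.960) = 0.885, or 89%. The figure reproduces. It is power for a mean difference, not for a slope, so it does not cover the graded test in any reading.

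**2. The data count.** Inputs from Section 13: 5 events per level, 5 to 7 levels, 10 off events, and a stated count above 30.

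| Points in a subject's regression | 5 levels | 6 levels | 7 levels |
|---|---|---|---|
| Active events only | 25 | 30 | 35 |
| Active events plus one averaged baseline | 26 | 31 | 36 |
| Active events plus 10 off events | 35 | 40 | 45 |
| Level averages, without / with baseline | 5 / 6 | 6 / 7 | 7 / 8 |

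Only the third row exceeds 30 throughout.

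**3. Slope produced by a flat on/off step.** Assumed coding: off = 0, active levels 1 to L, equally spaced. Let the PAT ratio be d higher at every active level, with no trend among them. The least-squares slope is c × d, where c = Σ(x − x̄)·1[x > 0] / Sxx and Sxx = Σ(x − x̄)².

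| L | x̄ | Sxx | c | Fitted rise, off to top (L × c × d) |
|---|---|---|---|---|
| 5 | 2.143 | 114.3 | 21.43/114.3 = 0.1875 | 0.94d |
| 6 | 2.625 | 179.4 | 26.25/179.4 = 0.1463 | 0.88d |
| 7 | 3.111 | 264.4 | 31.11/264.4 = 0.1176 | 0.82d |

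With one average per level and one for baseline, the rises are 0.71d, 0.64d and 0.58d. None of these figures needs a variance assumption. The true slope among active levels is zero in every case.

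**4. How often that slope would be significant.** Take the plan's 0.1 and 0.2 as the mean and between-subject SD (τ) of the on/off step. The event SD (σ) is not in the documents, so it is varied. A subject's slope has mean c × 0.1 and variance c²τ² + σ²/Sxx. The one-sample t-test on 40 slopes has noncentrality √40 × 0.1c / √(c²τ² + σ²/Sxx) on 39 degrees of freedom. For L = 5 and σ = 0.15 this is 6.325 × 0.01875 / √(0.001406 + 0.000197) = 2.96, giving 82%.

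| Assumed event SD | Significant positive slope, no trend among active levels (L = 5 to 7) |
|---|---|
| 0.10 | 85% |
| 0.15 | 82% |
| 0.30 | 68–69% |
| 0.50 | 47–49% |

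Simulation of the same setting gave about 84%, 67% and 47% at event SDs of 0.1, 0.3 and 0.5.

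The t-test on slopes is an added assumption, since the plan names only per-subject and combined regressions. A further simulation covered those (step 0.1, event SD 0.1 or 0.2, between-subject SD 0.1, SD of the observed on/off difference held at 0.2, 1,000 runs per setting):
- Individual subjects with a significant positive slope: 29–49% with the off events, 2.3–2.6% on active levels only (nominal 2.5%).
- Combined regression ignoring subject: significant in 95–98% of runs with the off events, 0–0.7% without.
- t-test on slopes: 83–86% with the off events, 4.7–5.7% without (nominal 5%).

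**5. Cost of separating the two contrasts.** Among active events alone Sxx is 50, 87.5 and 140 for L = 5, 6 and 7. For event noise, the standard error of the level term relative to the mixed slope is √(114.3/50) = 1.51, √(179.4/87.5) = 1.43 and √(264.4/140) = 1.37.

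For a truly linear rise of 0.1 from off to top level with between-subject SD 0.2, simulated power was 84% for the mixed slope and 79% for the active-level slope at event SD 0.15, and 73% and 60% at event SD 0.3.

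**The case against.** The strongest reply is that the plan never says that the off events are in the regression. Seven levels alone give 35 points, six give exactly 30, and the stated count may be loose. The sentence about averaging at each level would give only 5 to 7 points, which fits neither reading. This stands: inclusion is a strong inference from the count, not a stated fact, so the point is conditional. Averaging does not remove the problem, however (0.71d to 0.58d above).

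Second, a trend test that includes level zero is a valid test of the null that stimulation has no effect, and the aim itself is worded as the impact of stimulation. This also stands. The limit is on interpretation: such a test does not by itself support a graded claim among active levels.

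Third, nothing in the documents suggests a flat response, and a scheduled titration study presupposes some grading. A reader might infer from the calculation that no dose-response exists. It shows no such thing. The flat pattern is a scenario used to see what the test can tell apart.

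Fourth, the timeline has a home test on Night 1 and an in-lab titration on Day 45, so a reader might infer that off and active events come from different recordings with different means. The documents do not link either recording to the regression, and the off events could come from the titration night. A shift between recordings is possible but not established.

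Fifth, if the off events are left out, a reader might infer that the baseline goes unused. The 0.1 difference in the power statement reproduces as a within-subject mean difference, which suggests that an off/on comparison was intended, though no test for it is written out.

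**Conclusion.** The point holds in conditional form. Section 13 leaves the regression input unstated, and its own count fits 5 to 7 levels only with the off events included. On that reading a positive slope is evidence of an effect of stimulation, not of improvement across active levels.

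The fitted-rise figures rest only on off = 0 and equal spacing. The 47–84% range also rests on the assumed event SD, on reading 0.1 and 0.2 as the mean and SD of the on/off step, and on a t-test of subject slopes. It is therefore not a fixed property of the plan, although its direction is the same at every value tried.

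It would go too far to say that the Aim 1 analysis is invalid or that its result will be false. This is an inexpensive improvement that should be made because it changes what the primary analysis can conclude.

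**What to change.** In Section 13:

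- State whether the 10 off events enter the regression, how they are coded, whether events or level averages are the data points, and which recording supplies the off events. Correct the count if they are excluded.
- Give each subject's model two terms: an on/off indicator (off = 0, any stimulation = 1), and stimulation level centred among the stimulated events and set to 0 for off events. Carry the same two terms into the cohort analysis.
- Rest the graded Aim 1 claim on the level term alone.
- Report the on/off term as the mean PAT-ratio difference, and tie the stated 0.1 and 89% to it.

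This needs a change of wording and one extra model term, and no new data. The price is precision: the event-noise standard error of the level term is about 1.4 to 1.5 times that of the mixed slope, and power for a truly graded effect can fall, as the last step of the working shows. A reader might expect this loss to be offset because variation in the on/off effect leaves the level term. That holds only if the graded rise itself varies little between subjects, which the documents do not establish.
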